### 9.5.3 Analyses of Exploratory Efficacy Endpoint(s)

[REDACTED]

## 9.6 Safety Analyses

### 9.6.1 Analyses of Primary Safety Endpoint(s)

Subject incidence of DLTs will be used to fit the BLRM model to estimate the probability of having a DLT across dose levels at DLRM. Separate BLRM analysis will be conducted for each dose regimen, eg, MTD1 and MTD2 if there is one dose step. The BLRM analysis will be performed based on the Section 9.1 in Statistical Analysis Plan. Summary of the subject incidence of DLT will be provided.

### 9.6.2 Adverse Events

The Medical Dictionary for Regulatory Activities (MedDRA) version [24.0] or later will be used to code all events categorized as adverse events to a system organ class and a preferred term. The severity of each adverse event will be graded using CTCAE version 4.0 or later. For Cytokine release syndrome (CRS) events, grading is based on [Lee et al.](#)

[2014](#) for Cohort [REDACTED] and Etanercept substudy in FIH group; and is based on [Lee et al. 2019](#) for Cohort [REDACTED] onwards in FIH group, eIV group and MRD+ group, per protocol. The number and percentage of subjects reporting adverse events will be evaluated overall and by dose level and will also be tabulated by relationship to study drug.

The subject incidence of adverse events will be summarized for all **treatment-emergent adverse events (TEAE)**, treatment-related adverse events, serious adverse events (SAEs), grade 3 and above adverse events, adverse events leading to withdrawal of investigational product, adverse events leading to interruption of investigational product and fatal adverse events by system organ class, preferred term, and worst **severity** grade. Also, all TEAEs, **treatment-related adverse events**, SAEs and grade 3 and above adverse events will be summarized by preferred term only in descending order of frequency.

Treatment-emergent events of interest (EOIs) will be summarized by EOI category and preferred term. In addition, for each EOI category, the subject incidence of all, serious, grade 3 and above, fatal, leading to withdrawal of investigational product, leading to interruption of investigational product will be summarized.

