Subsequent eIV cohorts will use the same dose levels as the FIH (short IV) cohorts ([Table 4](#)). Dose escalation may occur if the DLRT deems that the eIV cohorts demonstrate a better benefit/risk profile than the equivalent FIH (short IV) cohorts. All other study processes remain unchanged. Data will be continuously evaluated, and DLRT may recommend dose schedule/level changes based on emerging PK data.

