3.1.3 Expansion Cohort

At completion of the dose escalation cohorts, approximately 90 additional subjects (approximately 40 R/R AML subjects in the FIH cohorts and 50 MRD+ AML subjects in the MRD+ cohorts) will be enrolled in dose expansion cohorts to gain further clinical experience, safety, and efficacy data in subjects with AMG 427. The dose to be evaluated will be at or below the MTD estimated in the dose escalation cohorts. Once the preliminary MTD and R2PD are established, the FDA will be provided with brief interim results of the dose escalation phase.

In the expansion phase, all available study data will be reviewed (with recruitment ongoing) by the DLRT once every 6th subject has at least completed their first treatment cycle plus 2 weeks or dropped out of treatment/study, whichever occurs earlier. The MTD will be further evaluated by applying BLRM using all available data, including data from subjects in the expansion phase. Ad hoc meetings may be convened any time in case of important safety events (see also Section 6.2.1.3).

Based on emerging safety data, the planned dose level and dose schedule may be modified during the conduct of the expansion phase. Additionally, enrollment to dose expansion will be paused and possibly terminated if safety stopping rules and/or efficacy futility rules are met (see Section 10.3 for details).

A final estimate of the MTD and RP2D using BLRM will be evaluated and confirmed utilizing all DLT-evaluable subjects from the dose escalation and the dose expansion cohorts. For definition of DLT-evaluable, see Section 6.2.1.3. Additional expansion cohorts testing alternative dose levels or biologic subsets may be considered by amendment.

The overall study design is described by a [Study Design and Treatment Schema](#) at the end of the protocol synopsis section.

The study endpoints are defined in Section 10.1.1.

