Hypotension	None	Not requiring vasopressors	Requiring a single vasopressor (not including vasopressin)	Requiring multiple vasopressors (not including vasopressin)
		And/or ^b		
Hypoxia	None	Requiring low-flow (≤ 6 L/minute) nasal cannula or blow-by	Requiring high-flow nasal cannula (> 6 L/min), facemask, non-rebreather mask, or Venturi mask	Requiring positive pressure (eg, CPAP, BiPAP, intubation and mechanical ventilation)

ASTCT = American Society for Transplantation and Cellular Therapy; BiPAP = bilevel positive airway pressure; CPAP = continuous positive airway pressure; CRS = cytokine release syndrome

Organ toxicities associated with CRS may be graded according to CTCAE v4.0 but they do not influence CRS grading.

^aFever is defined as temperature $\geq 38^{\circ}\text{C}$ not attributable to any other cause. In subjects who have CRS then receive antipyretic or anticytokine therapy such as tocilizumab or steroids, fever is no longer required to grade subsequent CRS severity. In this case, CRS grading is driven by hypotension and/or hypoxia.

^bCRS grade is determined by the more severe event: hypotension or hypoxia not attributable to any other cause. For example, a subject with temperature of 39.5°C , hypotension requiring 1 vasopressor, and hypoxia requiring low-flow nasal cannula is classified as grade 3 CRS.

Table 7. Management of Cytokine Release Syndrome

Description of CRS Severity ^a	Minimum Expected Intervention	Instructions for Interruption of AMG 427
Fever (temperature $\geq 38^{\circ}\text{C}$) without hypotension and hypoxia	
• Administer symptomatic treatment (eg, paracetamol/acetaminophen for fever).• Administer tocilizumab^b 4 to 8 mg/kg IV over 1 hour (not to exceed 800 mg). If no clinical improvement in signs and symptoms of CRS after the first dose, repeat tocilizumab every 8 hours (maximum of 3 doses in a 24-hour period; maximum total of 4 doses). If improving discontinue tocilizumab. Monitor for CRS symptoms including vital signs and pulse oximetry at least Q2 hours for 12 hours or until resolution, whichever is earlier. If symptoms of grade 1 CRS do not improve after 24 hours consider managing as grade 2.	

Page 1 of 4

Footnotes defined on next page of the table

Table 7. Management of Cytokine Release Syndrome

Description of CRS Severity ^a	Minimum Expected Intervention	Instructions for Interruption of AMG 427

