7.3.13 Events

[figure not shown]
Adverse event and serious adverse event assessments will be made throughout the study and will be evaluated and recorded in the source documents and on the eCRF as specified in Sections 9.2 and 9.1.1, respectively. The severity of all events will be graded according to CTCAE, version 4.0 ([Appendix A](#)) unless specified otherwise. Exception: CRS will be graded according to the adopted grading system referenced in Lee et al, 2019 (see [Table 6](#)) and ICANS will be graded according to the criteria referenced in the publication by Lee et al, 2019 (see [Table 8](#)).

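### SAP 9.6.2 pools CRS grades from two published scales in the FIH tables with no split, so FIH grade rates may fit neither scale, and any eIV-versus-FIH grade contrast needs a same-scale comparator

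*SAP*

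**What the plan says.** SAP 9.6.2 (Adverse Events) gives two grading rules for CRS. The 2014 published criteria apply to an early range of cohorts, with numbers redacted, "and Etanercept substudy in FIH group". The 2019 consensus criteria apply from a later redacted cohort "onwards in FIH group, eIV group and MRD+ group, per protocol".

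The same section sets the tabulation: "The number and percentage of subjects reporting adverse events will be evaluated overall and by dose level". Incidence tables cover, among others, grade 3 and above, and the list ends with "adverse events leading to interruption of investigational product and fatal adverse events by system organ class, preferred term, and worst" severity grade. Events of interest get their own summaries, again including grade 3 and above; the SAP does not list the categories, but CRS would be an obvious one. The section closes by reporting FIH, eIV and MRD+ separately. It gives no split by scale, no regrading and no sensitivity analysis, and SAP 10 declares no change from the protocol.

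The current protocol names one scale. Section 7.3.13 states: "CRS will be graded according to the adopted grading system referenced in Lee et al, 2019". Section 9.2.1.1 and Appendix A agree. The notes to Protocol Table 6 (Section 6.6) add: "Organ toxicities associated with CRS may be graded according to CTCAE v4.0 but they do not influence CRS grading".

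Protocol 3.1.1.2 (eIV Infusion Group) says: "Dose escalation may occur if the DLRT deems that the eIV cohorts demonstrate a better benefit/risk profile than the equivalent FIH (short IV) cohorts". Section 3.1.1.2.1 gives the eIV hypothesis as less intense or less frequent CRS symptoms.

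**The concern.** A grade is comparable only with grades made on the same scale. SAP 9.6.2 itself places both scales inside the FIH group, so an overall FIH rate of grade 3 or higher CRS mixes two definitions, and its value depends on how many subjects fall on each side of the switch. SAP 1 calls CRS the main on-target toxicity, so this is a table that readers will use.

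The second issue is conditional. eIV is graded only on the 2019 scale, and its escalation can turn on a judgement against the equivalent short-IV FIH cohorts. If those cohorts carry 2014 grades, a fall in CRS grade could come partly from the scale and not from the infusion.

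**Working it through.** **Are the scales interchangeable?** The 2014 criteria are not reproduced, so only indirect evidence is available.

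- 2019 scale: Table 6 grades on fever, hypotension and hypoxia, and its notes exclude organ toxicity.
- Trial history: the amendment 5 rationale reports one DLT, a grade 3 CRS, with a grade 4 ALT that did not resolve to grade 1 within 7 days given in brackets as its description.

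On the 2019 scale that event's CRS grade would depend only on fever, hypotension and hypoxia. This suggests that the older grade could be higher for the same event. It is one event, and that the grade rested on the ALT is an inference.

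**How many subjects could carry the older scale?**

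- Given AMG 427 by 26 July 2021: 51 (Protocol 2.2.4). The total of 53 includes 2 who received etanercept only; the Safety Analysis Set requires a dose of AMG 427 (SAP 6.2).
- Planned FIH escalation: about 90, including the etanercept substudy (90 + 10 eIV + 10 MRD+ = 110).
- Upper bound: 51/90 = 57%. Section 2.2.4 mentions one further treated subject without exposure data; adding that subject gives 52/90 = 58%.
- If the FIH tables also take in the 40 expansion subjects: 51/130 = 39%.

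These shares assume that the switch did not precede the cut-off and that nobody dosed later carries a 2014 grade.

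**What could mixing do?** The plan states no figure to reproduce, so this is an illustration. Assumptions not in the documents: true severity is identical; p is the grade 3 or higher rate on the 2014 scale (5% to 30%); r is the share of those events that fall below grade 3 on the 2019 scale (0, 25% or 50%).

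*Pooled FIH rate*, with 51 old-scale and 39 new-scale subjects (split assumed), p = 15%, r = 50%:

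(51 × 0.150 + 39 × 0.075)/90 = (7.65 + 2.925)/90 = 11.75%.

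The single-scale rates would be 15.0% and 7.5%; the pooled rate is neither.

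*eIV against FIH*, if the comparator is on the 2014 scale. The expected spurious fall is p × r. The chance that eIV looks lower, with 10 subjects on each side, is the sum over j < i of Bin(i; 10, p) × Bin(j; 10, p(1 − r)).

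| p | r | p × r (points) | P(eIV lower) | P(eIV higher) |
|---|---|---|---|---|
| 5% | 0 | 0 | 0.27 | 0.27 |
| 5% | 50% | 2.5 | 0.33 | 0.14 |
| 15% | 0 | 0 | 0.37 | 0.37 |
| 15% | 25% | 3.75 | 0.46 | 0.27 |
| 15% | 50% | 7.5 | 0.56 | 0.17 |
| 30% | 0 | 0 | 0.40 | 0.40 |
| 30% | 50% | 15 | 0.71 | 0.14 |

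On one scale (r = 0) the comparison is symmetric and the artefact is zero.

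**The case against.** A reader might infer that the eIV comparison is biased. The documents do not show that. The cohort at which the scale changes is redacted, so the scale of the equivalent short-IV cohorts is unknown; if it is the 2019 scale, the comparison is clean. The amendment 7 summary lists the move to the consensus tables, which points to a late switch. Against this, bold type appears to mark text new in amendment 7, and the 2019 citations for CRS in Protocol 6.6 and 9.2.1.1 are not bold, so an earlier switch is possible. There is also no formal eIV-versus-FIH test, and the Dose Level Review Team sees vital signs, laboratory data and concomitant medication as well as grades (Protocol 10.4.2).

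A reader might also infer that the dose-toxicity model is contaminated, because CRS grade enters the DLT definition and the final MTD is estimated "utilizing all DLT-evaluable subjects from the dose escalation and the dose expansion cohorts". That is unproven. Protocol 6.2.1.3 separately counts grade 3 to 5 non-hematologic toxicity, with listed exceptions, so the amendment 5 event could remain a DLT whatever its CRS grade. SAP 9.1 and 9.6.1 also fit a separate model for each dose regimen.

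The reference to the protocol in SAP 9.6.2 need not be an error: early cohorts were treated under earlier protocol versions, and the SAP discloses the rule openly. Dose-level columns may partly separate early from late cohorts.

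What stands is the pooling inside FIH. Reporting the three groups separately does not remove it, because both scales sit in one of them.

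**Conclusion.** The point holds for the FIH tables. As written, SAP 9.6.2 yields FIH CRS rates by grade that combine two scales which the documents indicate are not interchangeable. Up to about 57% of planned FIH escalation subjects could carry the older scale, on the timing assumptions above. The size and direction of the shift are not known; direction rests on the Table 6 note and one historical event.

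For eIV against FIH the point is conditional on the comparator cohorts having 2014 grades. Two larger figures are tempting and should not be used. Taking 53 of 90 (59%) counts two subjects who never received AMG 427. Saying that one reclassified subject moves an eIV cohort of 2 to 4 by 25 to 50 points does not apply, because eIV subjects are already on the 2019 scale and none would be reclassified. No effect on the MTD is shown.

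**What to change.** Amend SAP 9.6.2 as follows.

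1. Present FIH CRS by grade separately for each scale in the overall, worst-grade, grade 3 and above and events-of-interest tables. Do not pool grades across scales.
2. Where collected data allow, derive a 2019-scale grade for early events, use it for pooled FIH tables, and keep the grade as recorded in a listing.
3. Limit eIV-versus-FIH comparisons of CRS grade to cohorts on the same scale or with derived 2019 grades. Otherwise use scale-free measures: any CRS, or use of vasopressors, oxygen or tocilizumab.
4. Keep the original DLT calls in the primary model. At most, add a sensitivity run for any DLT that depended only on a 2014-scale CRS grade.

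The cost is SAP wording, one derivation and slightly more tables. Temperature, oximetry and concomitant therapies are collected (Protocol 7.3.4, 7.3.9 and 7.3.10), but the documents do not show that oxygen device and flow or the number of vasopressors are recorded for each event. Some early events may not be gradable on the 2019 scale and would stay in the separate 2014 column.

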**The safety analysis will be provided for FIH, eIV and MRD+ groups separately.**

### **9.6.3 Laboratory Test Results**

Clinical chemistry, hematology, and urinalysis data will be presented and reviewed for each subject in DLRM. Values outside the normal laboratory reference ranges will be flagged as high or low on the listings.

Summaries of the absolute value and/or changes from baseline at each scheduled assessment may be provided for selected laboratory parameters of interest.

Shifts tables indicating the change between the baseline and the maximum post dose CTCAE grades (CTCAE version 4.0 or later) for an increased value, and the maximum post dose grade for a decreased value will be provided for selected laboratory parameters of interest.

### **9.6.4 Vital Signs**

Vital signs data will be listed and reviewed for each subject in DLRM. Depending on the size and scope of changes, summaries of vital signs data over time and/or changes from baseline over time may be provided.

[figure not shown]
### **9.6.5 Physical Measurements**

NA

### 9.6.6 Electrocardiogram

All on-study electrocardiogram (ECG) data will be listed and selected parameters of interest may be presented using mean plots.

Summaries over time and/or changes from baseline over time will be provided for PR, QRS, QT, QTc, RR.

### 9.6.8 Exposure to Investigational Product

Descriptive statistics will be produced to describe the exposure to investigational product by treatment group. The number of cycles **started**, number of doses of investigational product, **cumulative dose**, **cumulative dose per cycle**, the total dose and duration of exposure will be summarized.

Details for each AMG 427 administration will be listed for every subject. In addition, a listing of the unique manufacturing lot numbers, and a listing of the subjects administered each manufacturing lot number will be provided.

### 9.6.9 Exposure to Non-investigational Product

NA

### 9.6.10 Exposure to Other Protocol-required Therapy

Descriptive statistics will be produced to describe the exposure to dexamethasone. The number of doses of dexamethasone and the total dose in mg will be summarized.

### 9.6.11 Exposure to Concomitant Medication

The number and proportion of subjects receiving concomitant medication will be summarized by preferred term as coded by the World Health Organization Drug (WHO DRUG) dictionary.

## 9.7 Other Analyses

Analysis for the Enbrel substudy will be described in Supplemental Statistical analysis plan (SSAP).

### **9.7.1 Analyses of Pharmacokinetic or Pharmacokinetic/Pharmacodynamic Endpoints**

Serum concentrations of AMG 427 will be determined using a validated assay. PK parameters will include, but are not limited to half-life ( $t_{1/2}$ ; if feasible), maximum observed concentration ( $C_{max}$ ), minimum observed concentration ( $C_{min}$ ) and area under the concentration-time curve from time 0 to the time of the last quantifiable concentration ( $AUC_{0-last}$ ). Pharmacokinetic parameters will be estimated using standard non-compartmental approaches and summarized by dose level using means, standard deviations, medians, minimums, and maximums.

Serum concentrations below the lower limit of quantifications will be set to zero for the estimation of the pharmacokinetic parameters for each subject and for the calculation of the summary statistic for each time point. Actual dosing and sampling time will be used for all calculations. The reasons for excluding any sample from the analyses will be provided.

Individual concentration-time data will be summarized by dose level. Individual concentration-time data will also be tabulated and presented graphically. Summary statistics will be computed for each sampling time and parameter as appropriate. Additional PK analyses, including but not limited to analysis of the relationship between AMG 427 dose and exposure parameters ( $AUC$  and  $C_{max}$ ) and dose proportionality assessments, may also be conducted. Based on the review of the data, analyses to describe the relationship between AMG 427 exposure and either Pharmacodynamic effect and/or clinical outcome may also be performed.

### **9.7.2 Analyses of Clinical Outcome Assessments**

NA

### **9.7.3 Analyses of Health Economic Endpoints**

NA

### **9.7.4 Analyses of Biomarker Endpoints**

Analyses of biomarker endpoints will be performed by Clinical Biomarker and Diagnostics (CBD) function and details will be captured in a separate data analysis plan.

## **10. Changes From Protocol-specified Analyses**

There are no changes to the protocol-specified analyses.

**12. Prioritization of Analyses**

NA

**13. Data Not Covered by This Plan**

NA

14. Appendices

Appendix A. Reference Values/Toxicity Grades

NA

## Appendix B. Concomitant Medications

NA

### Appendix C. Clinical Outcome Assessment Forms/Instruments

NA

## Appendix D. Health Economic Forms/Instruments

NA

## Appendix E. Details of PK or PK/PD Methods for Modeling

NA

## Appendix F. Analytical Windows

NA

### Appendix G. Handling of Dates, Incomplete Dates and Missing Dates

Below imputation rules will be used to impute start date and stop date of AE and Concomitant medication. Date of prior anti-cancer therapy, PD-1, PD-L1 and metastasis will be imputed using the same rule when only the date is missing (no imputation when month or year is missing).

#### Imputation Rules for Partial or Missing Start Dates

The reference date for the following rules is the date of first dose[ of study drug].

Start Date		Stop Date						Missing
		Complete: yyyyymmdd		Partial: yyyyymm		Partial: yyyy		
		< 1 st dose	≥ 1 st dose	< 1 st dose yyyyymm	≥ 1 st dose yyyyymm	< 1 st dose yyyy	≥ 1 st dose yyyy	
Partial: yyyyymm	= 1 st dose yyyyymm	2	1	n/a	1	n/a	1	1
	≠ 1 st dose yyyyymm		2	2	2	2	2	2
Partial: yyyy	= 1 st dose yyyy	3	1	3	1	n/a	1	1
	≠ 1 st dose yyyy		3	3	3	3	3	3
Missing		4	1	4	1	4	1	1

1=Impute the date of first dose; 2=Impute the first of the month; 3=Impute January 1 of the year; 4=Impute January 1 of the stop year

Note: For subjects who were never treated (first dose date is missing), partial start dates will be set to the first day of the partial month or first day of year if month is also missing.

#### Imputation Rules for Partial or Missing Stop Dates

##### Initial imputation

- If the month and year are present, impute the last day of that month.
- If only the year is present, impute December 31 of that year.
- If the stop date is entirely missing, assume the event or medication is ongoing.

If the imputed stop date is before the start date, set stop date to missing.

If the imputed stop date is after the death date, impute as death date.

#### Imputation Rules for Partial or Missing Death Dates

If death year and month are available but day is missing:

- If **yyyymm** for the date last known to be alive equals **yyyymm** for death date, set death date to the day after the date last known to be alive.
- If **yyyymm** for the date last known to be alive is less than the **yyyymm** for death date, set death date to the first day of the death month.
- [If **yyyymm** for the date last known to be alive is greater than **yyyymm** for death date, assume date last known to be alive is in error, set death date to the first day of the death month.

If month and day are missing and year of death is known:

- If **yyyy** for the date last known to be alive equals **yyyy** for death date, set death date to the day after last known to be alive date.
- If **yyyy** for the date last known to be alive is less than **yyyy** for death date, set death date to the first day of the death year.
- If **yyyy** for the date last known to be alive is greater than **yyyy** for death date, assume date last known to be alive is in error, set death date to the first day of the death year.

If a death date is totally missing:

Do not impute and censor the subject survival time.

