12.4 Investigator Responsibilities for Data Collection

The investigator is responsible for complying with the requirements for all assessments and data collection (including subjects not receiving protocol-required therapies) as stipulated in the protocol for each subject in the study. For subjects who withdraw prior to completion of all protocol-required visits and are unable or unwilling to continue the Schedule of Assessments ([Table 10](#) to [Table 23](#)), the investigator can search publicly available records [where permitted] to ascertain survival status. This ensures that the data set(s) produced as an outcome of the study is/are as comprehensive as possible.

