### 2.1 Objectives and Endpoints

[figure not shown]
Objectives	Endpoints
Primary	

• Evaluate the safety and tolerability of AMG 427 in adult subjects with relapsed/refractory (R/R) AML or minimal/measurable residual disease-positive (MRD+) AML

• Estimate the maximum tolerated dose (MTD) and / or a biologically optimal dose (eg, recommended phase 2 dose [RP2D])

• Evaluate the safety and tolerability of extended intravenous (eIV) administration of AMG 427

	

• Safety: Dose-limiting toxicities (DLTs), treatment-emergent adverse events (TEAEs) and treatment-related adverse events (TRAEs)

Secondary	

Characterize the pharmacokinetics (PK) of AMG 427

	

AMG 427 PK parameters including, but not limited to, maximum serum concentration (<math>C_{max}</math>), minimum serum concentration (<math>C_{min}</math>), area under the concentration-time curve (AUC), and if feasible, half-life (<math>t_{1/2}</math>) of AMG 427

Evaluate the anti-leukemia activity of AMG 427

	

Efficacy parameters for (R/R) AML: Subject response to treatment with AMG 427 (response defined as complete response/remission [CR] / complete response/remission with incomplete recovery of peripheral blood counts [CRi] / morphologic leukemia-free state, partial remission [per modified International Working Group (IWG) criteria], complete response/remission with partial hematologic recovery [CRh]) and duration of response (duration of response will only be measured for subjects in the expansion cohort).

Efficacy parameters for MRD+ AML: Subject response to treatment with AMG 427 (response refers to conversion from MRD + status to MRD - status), relapse free survival,

	
and overall survival (relapse free survival and overall survival will only be measured for subjects in expansion cohort).

--	--

Exploratory

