#### Dose expansion cohorts:

- **FIH (R/R AML): approximately 40 subjects**
- **MRD Group (MRD+): approximately 50 subjects**

The sample size in the dose escalation is based on practical considerations and is consistent with conventional oncology studies with the objective to estimate the MTD.

With 2 subjects per cohort, there is a 19% to 55% probability of observing at least 1 DLT. With 3 subjects per cohort, there is a 27% to 70% probability of observing at least 1 DLT if the true DLT rate is 10% to 33% and with 4 subjects per cohort, there is a 34% to 80% probability.

In the dose expansion cohort, a subject number of 40 will provide an 87% probability of observing at least 1 adverse event with 5% incidence rate and 99% probability of observing at least 1 adverse event with 10% incidence rate. **A subject number of 50 will provide a 92.3% probability of observing at least 1 adverse event with 5% incidence rate and 99.5% probability of observing at least 1 adverse event with 10% incidence rate.** These probabilities will be 64% and 88% respectively with a subject number of 20. An exact 80% binomial confidence interval (CI) will be provided for response rate. With the 20 subjects and 20% response rate, the expected 80% CI would be 9% to 36%. With 40 subjects and 20% response rate, the expected 80% CI would be 12% and 30%. **With 50 subjects and a 40% response rate, the expected 80% CI would be 30.6% and 50.1%.**

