Overall survival (OS) is defined as the time from the start of treatment (Study day 1) until event of death due to any cause.

OS time (Days) = Date of death – Study Day 1 + 1

OS time (Months) = (Date of death – Study Day 1 + 1)/30.4

Subjects still alive will be censored at the date last known to be alive. If the date last known to be alive is after the date that triggers the analysis (ie, the data cutoff date), the subject will be censored at the analysis trigger date.

Relapse-free Survival (RFS) (for MRD+ group)

RFS time will be calculated from the date of first administration of AMG 427 until the date of a hematologic relapse or death, whichever occurs first. Subjects still alive and relapse-free will be censored on their last disease assessment date.

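### SAP Appendix G censors overall survival for known deaths that have no date, against the SAP's own definition of overall survival

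*SAP*

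**What the plan says.** SAP Section 5 (Overall Survival) defines the endpoint: "Overall survival (OS) is defined as the time from the start of treatment (Study day 1) until event of death due to any cause". Its censoring rule covers the living: "Subjects still alive will be censored at the date last known to be alive", or the analysis trigger date if that comes first.

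SAP Appendix G (Imputation Rules for Partial or Missing Death Dates) then treats incomplete dates in two ways.

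- **Year, or year and month, known:** the death stays an event. If the known part matches the last-alive date, the rule is to "set death date to the day after the date last known to be alive" (the year-only branch is equivalent). In the other branches death is placed on the first day of the death month or year.
- **Nothing known:** "Do not impute and censor the subject survival time". No censoring date is given.

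OS is a secondary endpoint listed under MRD+ AML, and SAP Section 2.1 limits it: "relapse free survival and overall survival will only be measured for subjects in expansion cohort". SAP Section 3.2 plans the size: "MRD Group (MRD+): approximately 50 subjects". SAP Section 9.5.2 reports Kaplan-Meier curves and rates with 80% confidence intervals. The SAP text describes no sensitivity analysis for undated deaths.

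**The concern.** Appendix G's rule sits under a heading about death dates, so it concerns subjects known to be dead. Section 5 counts those subjects as events and has no censoring route for them. A programmer following one section departs from the other, and anyone who censors must also choose the date.

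Kaplan-Meier estimation assumes that a censored subject has the same prognosis as those still at risk. A subject censored because of an undated death is known to have died after last contact. Dropping such events lowers the estimated hazard. The scenario is conceivable here: long-term follow-up is by telephone (Protocol Section 7.2.5), and for subjects who withdraw, "the investigator can search publicly available records [where permitted] to ascertain survival status" (Protocol Section 12.4), which mentions status and not a date.

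What is at stake is the accuracy of the OS curve in the MRD+ expansion cohort.

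**Working it through.** The documents give no OS median, event count or survival rate, so there is no planned OS figure to reproduce. The check is the conflict above plus a sizing exercise.

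**From the documents:** about 50 subjects (SAP 3.2); contact every 8 weeks for at most 2 years from first dose (Protocol 7.2.5); Kaplan-Meier with 80% intervals (SAP 9.5.2).

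**Assumed:** exponential survival with median 6, 12 or 18 months; 2% to 20% of deaths undated, at random; censoring at the last 8-weekly contact before death.

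**Step 1, one death by hand.** Take 50 subjects and 30 deaths evenly spaced over 24 months. With all dates known, 24-month OS is 20/50 = 0.400. Let the 15th death be undated and censored at the preceding contact, with no other death in between. After 14 deaths the estimate is 36/50 = 0.720, with 35 subjects left at risk, of whom 15 die. So 24-month OS = 0.720 × 20/35 = 0.411, a rise of 1.1 points. With three undated deaths it becomes 0.438.

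**Step 2, approximation.** If a random fraction m of deaths is censored close to the time of death, the estimated hazard is (1 − m) times the true one, so the curve tends to S(t)^(1−m). True 12-month OS is 2^(−12/median). For a 12-month median this is 0.500, giving 0.500^0.95 = 0.518 at m = 5% and 0.500^0.90 = 0.536 at m = 10%.

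**Step 3, simulation.** Mean 12-month Kaplan-Meier OS over 3,000 trials of 50 per setting, with 24-month administrative censoring:

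| Median OS (months) | Undated | All dates known | Appendix G rule | Shift (points) | Event on day after last alive |
|---|---|---|---|---|---|
| 6 | 5% | 0.250 | 0.266 | +1.6 | 0.248 |
| 6 | 10% | 0.249 | 0.283 | +3.4 | 0.247 |
| 12 | 5% | 0.500 | 0.517 | +1.7 | 0.499 |
| 12 | 10% | 0.501 | 0.536 | +3.5 | 0.499 |
| 18 | 5% | 0.630 | 0.644 | +1.4 | 0.629 |
| 18 | 10% | 0.630 | 0.659 | +2.9 | 0.628 |

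The simulation agrees with the approximation. At 2% undated (fewer than one death lost on average) the shift is 0.6 to 0.7 points; at 20% it is about 6 to 7. At a 12-month true median, the typical estimated median OS moves from 11.7 to 12.5 months (5%) or 13.3 months (10%).

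**Step 4, the alternative.** Keeping the death as an event on the day after last known alive nearly removes the shift. The largest residual error seen is downward: 0.486 against 0.501 for 6-month OS with 20% undated and a 6-month median, about 1.5 points.

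**Scale.** A normal-approximation 80% interval at 0.50 with 50 subjects is ±1.282 × √(0.25/50) = ±9 points.

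**The case against.** The strongest reply is that this will rarely happen and matters little. A totally missing date means that not even the year is known. Expansion subjects are contacted every 8 weeks, and fatal events in the reporting period must be submitted within 24 hours (Protocol Sections 9.1.2 and 9.2.1.2), so for subjects in follow-up a partial-date rule would normally apply. Protocol Section 12.4 does not say that public records give status without a date. No OS test is planned, no stopping rule uses OS, and the shift at 5% or 10% undated is well inside the 80% interval. All of this stands, and it limits the size of the point. It does not reconcile Appendix G with Section 5.

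A reader might also infer more than the documents support:

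- **That relapse-free survival and duration of response are overstated too.** Death is an event in both, but each has its own censoring date based on disease assessment. Appendix G does not say whether its reference to survival time covers them.
- **That the estimate is raised at every time point.** Between last contact and the true death the risk set is one smaller, so other deaths in that gap lower the curve slightly. The upward shift holds on average.
- **That the SAP already dates partial deaths the day after last contact.** It does so only in the branches where the year or month matches, and every branch has at least a year. Using that anchor with no date information extends the rule.
- **That 5% or 10% is expected.** These rates are illustrations.

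The first-of-month and first-of-year rules tend to date deaths early, a small opposite bias, but they do not restore a lost event.

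**Conclusion.** The conflict is certain: Section 5 counts every death and censors only the living, while Appendix G censors some known deaths and names no date for doing so. The resulting censoring is informative and on average raises Kaplan-Meier OS in the MRD+ expansion cohort. The size is conditional: roughly 1.5 points at 12 months if 5% of deaths are undated, 3 to 3.5 points if 10% are, zero if none are. Those figures rest on exponential survival, dates missing at random, and contact every 8 weeks until death. They do not describe a subject who withdrew long before dying. The consequence is confined to a descriptive secondary endpoint. The change is worth making because the inconsistency is plain and the cost is slight.

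**What to change.** In SAP Appendix G, replace the instruction for totally missing death dates:

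1. Count every confirmed death within the OS follow-up and data cutoff as an event. Either date it the day after last known alive, extending the anchor used in the matching-year and matching-month branches, or treat it as interval-censored between last known alive and the date the death was learned.
2. Report the number of such subjects.
3. Show censoring at the date last known alive as a sensitivity analysis.
4. State whether the rule also applies to deaths in relapse-free survival and duration of response.

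The cost is a few sentences in the SAP and one extra analysis. The downside is that day-after dating may place some events too early. The resulting downward bias was at most about 1.5 points in the settings tried. It could be larger for a subject whose death is learned long after withdrawal, and there the interval-censored option fits better.
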